7.3. Full Analysis Set (FAS), Immunogenicity

FAS-1: Booster immunogenicity analysis

All subjects in the Enrolled Set who receive at least one booster dose during the trial (because RVNA value below 0.5 IU/mL at scheduled visit) or before entering the trial (e.g. travellers to endemic areas or veterinarians who got the booster regardless of the RVNA value) and provide immunogenicity data.

FAS-2: Long term immunogenicity analysis

All subjects in the Enrolled Set who provide immunogenicity data.

Note: In the long-term immunogenicity analysis, when a subject receives a rabies vaccine booster dose (before or during the study) because RVNA value is below 0.5 IU/mL, subsequent RVNA values after the booster dose will be set to half of the detection level (i.e. 0.1 IU/mL) until study end even if the subject withdraws earlier than last study visit (see last part of section [8.2](#) for a detailed explanation).

In case a subject receives a booster dose before or after entering the study (e.g. travellers to endemic areas, veterinarians) but the last known RVNA value was above 0.5 IU/mL, then he/she will be excluded from the long term immunogenicity analysis set (i.e. FAS-2 and PPS). This is justified by the fact that including actual values as recorded after the booster dose would inflate the immunogenicity persistence; on the other hand, it would be inappropriate to apply the same rule used for subjects receiving a booster dose when RVNA value is less than 0.5 IU/mL as this is not the case.

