8.2. Handling of Dropouts, Missing Data

Time to event analysis:

The Cox proportional hazards regression model analysis will be based on methods for right-censored data ([Lindsey](#), 1998).

In this setting, the event/failure will be represented by having a RVNA concentration <0.5 IU/mL (see section [8.8](#)). Subjects without event (with missing blood draw, or lost to follow up or early terminated) will be regarded as right-censored data.

GMC and percentage analysis - boostability:

To evaluate the booster response in terms of Geometric Mean Concentration (GMC), Geometric Mean Ratio (GMR) and percentage of subjects with RVNA concentration ≥ 0.5 IU/mL; missing data will be not included in the analysis.

GMC and percentages of subjects with RVNA concentrations ≥ 0.5 IU/mL

To evaluate the long-term (up to approx.10 years) immunogenicity in subjects who received a primary series of accelerated or conventional rabies PrEP in the parent study (V49_23) in terms of GMC and percentage of subjects with RVNA concentration ≥ 0.5 IU/mL; missing data as such will be not included in the analysis. If a subject receives a rabies vaccine booster dose, the RVNA value after booster will be set to half of quantification level from that moment onward. This because the exposure to a booster dose during the trial introduces a bias, as the RVNA concentrations will reflect the booster response and not the long-term persistence after the primary series (i.e., vaccination received at time of parent study).

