8.2.2. Immunogenicity Data

Immune response in subjects with or without booster will exclude missing values, assuming missing immunogenicity values as Missing Completely At Random (MCAR) and therefore will not contain information that impact the result of the analysis (i.e., not informative).

Imputation methods will be used for those subjects who will receive a booster dose during the trial i.e., once the RVNA concentration fall below the predefine cut-off of 0.5 IU/mL, that value will be set up to half of quantification level from that moment onward.

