All further subject immunogenicity data will not be used for Time to event analysis.

GMC and percentage analysis - boostability:

Subject is included in the Exposed to Booster Set and independently on time or visit in which booster is administered the time-points will be as following:

- Pre-booster
- 7 days after booster
- 6 to 9 months after booster

Long-term persistence of antibody responses after primary series

All immunogenicity data until booster will be part of analysis as they are reported.

For subjects receiving a booster dose, the following method of imputation will be used for antibody values:

- Values, missing or not, will be replaced with half of the quantification level (0.1 IU/mL) from that moment onward.

Subjects receiving a booster dose outside of the study and for which RVNA value at the time of booster vaccination is not available will be excluded from FAS-2 and PPS-2 (see section 7.3 for details)

Duration in the Study

Duration in the study is defined in days as:

Last visit date (visit x)^a – Enrollment date (visit 1) + 1

^a or premature discontinuation date (in case of withdrawal from the study)

The duration is missing if one of the dates is missing or incomplete.

Unsolicited Serious Adverse Events

All serious adverse events (AEs) following *Rabipur* booster dose within the study will be characterized according to the date of occurrence related to the vaccination phase as follows:

- **Emergence before vaccination phase:** start date before the first date of injection of study vaccine.
- **Emergence during vaccination phase:** start date on or after the first date of injection of study vaccine or, adverse event increase in severity including to “serious” AE.

If start date is equal to the first date of injection then “timing” variable (“On injection day, before injection”/“On injection day, after injection”) will be used to define whether the adverse event occur before or after the injection.

If an AE start date is missing or unknown, the AE will be considered as emergent.

When start and/or end dates of an AE are only partially known, AEs will be categorized as emergent before, during, or after vaccination phase using the following rules:

- If the partial end date is before ($<$) the first study vaccination (i.e., year or year & month is/are before the first study vaccination year or year & month) then the AE is emergent before vaccination phase.

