11.3. Secondary Objectives Analysis

Secondary Immunogenicity Objective:

To evaluate the long-term (up to approx.10 years) immunogenicity in subjects who received a primary series of accelerated or conventional rabies PrEP intramuscular (IM) regimen in the parent study V49_23.

Yearly Geometric Mean Concentrations up to Year 10

All subjects enrolled in this extension study, independently from booster administration, are planned to be followed until year 10 from the primary vaccination.

Log-transformed antibody titers as collected at annual Scheduled Clinic Visits (from Visit 1 to Visit 7) will be analyzed using a mixed model for repeated measures within subject, including time, center and treatment as independent variables, interaction for time and treatment, a random intercept with an unstructured covariance matrix.

SAS code will look like the following:

```
PROC MIXED DATA = model;
  class subject time treatment center;
  model log_Ab = time treatment time*treatment center/ CL s ;
  lsmeans time treatment time*treatment;
  random intercept / subject = usubjid type = UN;
RUN;
```

Reverse Cumulative Distribution Figure (RCDF) up to Year 10

The percentages of subjects with concentration greater than or equal to defined RVNA values (on log10 scale) will be presented as reverse cumulative distribution curve, having the individual RVNA concentration on the X-axis and the percentage of subject with equal to or greater than the value on the Y-axis by each study visit (i.e., Year)

Note: If subject receives a booster during the study, for the purpose of the secondary objective analysis on long-term persistence of immune responses the RVNA concentration after the booster will not be 'entered' as such, but half of quantification level from that moment will be used for all consecutive visits.

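### Boosted subjects are held at 0.1 IU/mL even after withdrawal while unboosted dropouts are left out, so the yearly % ≥0.5 is too low under the SAP's own MCAR assumption; the floor also distorts the lower RCD curve and, usually, the GMCs

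*SAP*

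**What the plan says.** SAP 7.3 (FAS-2 note) covers subjects boosted because RVNA was below 0.5. Their later values "will be set to half of the detection level (i.e. 0.1 IU/mL) until study end even if the subject withdraws earlier" than the last study visit. SAP 8.8 repeats the rule: "Values, missing or not, will be replaced with half of the quantification level (0.1 IU/mL) from that moment onward". SAP 11.3 applies it to the secondary persistence analyses: "half of quantification level from that moment will be used for all consecutive visits".

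For everyone else, SAP 8.2 says that "missing data as such will be not included in the analysis", and 8.2.2 justifies this by MCAR. SAP 8.2 gives the reason for the floor: real post-booster titres show the booster response, not persistence after the primary series.

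The protocol treats the same analyses differently. Sections 8.3.4 and 8.4.3.3.3 drop subjects once they have been boosted.

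The wording also disagrees on details:
- **Assay limit.** 7.3 calls 0.1 half the detection level; 8.8 calls it half the quantification level. Yet the 8.8 program lists <0.1 as a result code, and 8.8 sets values below the quantification limit to half that limit.
- **Triggering value.** 8.2.2 says of the value that fell below 0.5 that "that value will be set up to half of quantification level from that moment onward". 8.8 says "All immunogenicity data until booster will be part of analysis as they are reported".
- **Censoring.** One sentence in 8.8 sets the indicator to 0 at the first titre below 0.5, although 1 is defined as the event.

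The time-to-event analysis does not use the floor: "All further subject immunogenicity data will not be used for Time to event analysis".

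**The concern.** Failures and persisters leave the yearly denominator by different rules. A subject boosted for RVNA <0.5 can never leave. A subject still at or above 0.5 leaves on dropping out. The longer the follow-up, the more the denominator fills with failures who are no longer observed.

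The floor raises a second, separate issue. A triggering result may be 0.2, 0.3 or 0.4, but every later value is entered as 0.1. The reason in 8.2 justifies discarding post-booster titres. It does not justify a particular replacement value, or filling visits after withdrawal.

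Yearly GMCs, RCD curves and percentages ≥0.5 are the secondary endpoints (protocol 8.1.2.3). SAP 14.1 allows the interim report to go to a Health Authority on booster timing, so understated persistence could matter. The planned Kaplan-Meier curves offer a check on the percentage, but nothing planned checks the GMCs or the lower RCD curve.

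**Working it through.** The plan states no figure to reproduce and gives no titres, dropout rate or booster uptake. The direction follows from the rules. Every size below rests on assumed values.

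**1. Yearly %, simplest case.** Take 100 subjects: 70 truly ≥0.5, 30 failures boosted early, then 30% dropout in everyone.
- SAP rule: 70 × 0.7 = 49 persisters remain and all 30 failures stay, so 49/(49 + 30) = 62.0%.
- Imputation stopped at withdrawal: 49/(49 + 21) = 70.0%.

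**2. Yearly % at Year 10, closed form.** Let S be the true share ≥0.5, r the share retained, N the new failures at Year 10, and B the failures boosted before dropout, who are never removed. The SAP estimate is S·r/(S·r + N·r + B).

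Example: 70% at Year 3, 3% of persisters failing each year, 5% yearly dropout, boosting taken at the failing visit.
- S = 0.70 × 0.97^7 = 0.566; r = 0.95^7 = 0.698; N = 0.70 × 0.97^6 × 0.03 = 0.0175.
- B = 0.30 + Σ(k = 1 to 6) 0.70 × 0.97^(k−1) × 0.03 × 0.95^k = 0.399.
- Estimate = 0.395/(0.395 + 0.012 + 0.399) = 49.0%, against a true 56.6%.

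Loss over Year-3 shares of 50–90% and yearly failure of 2–5%:

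| Yearly dropout | Loss at Year 10 (points) |
|---|---|
| 0% | 0 |
| 3% | 2.7–4.9 |
| 5% | 4.7–8.2 |
| 10% | 10.7–16.6 |

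A titre simulation (two arms, assumed Year-3 GMCs of 4.0/2.5, 2.0/1.2 and 0.8/0.45; log10 SD 0.40 between subjects, residual 0.18, mean slope −0.03 per year) gave smaller losses: 1–4 points at 3%, 3–8 at 6% and 5–13 at 10%. The arm gap at 6% dropout moved either way: 12 to 15 points in the high case, 18 to 15 in the low case.

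**3. RCD curve below 0.5, no dropout.** Every boosted subject sits at 0.1, below any cut-off above 0.1. In the middle case (2.0/1.2) the share ≥0.25 at Year 10 falls from 93/85% to 72/52%.

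**4. GMC, no dropout.** If 10% of an arm is boosted, replacing a trigger value t by 0.1 multiplies a crude GMC by (0.1/t)^0.1. All five result codes in 8.8, with <0.1 scored as 0.05:

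| Trigger | Change in crude GMC |
|---|---|
| <0.1 (0.05) | +7.2% |
| 0.1 | 0 |
| 0.2 | −6.7% |
| 0.3 | −10.4% |
| 0.4 | −12.9% |

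This holds the trigger value flat. With a decline of 0.03 log10 per year, 0.2 becomes 0.2 × 10^(−0.18) = 0.13 after six years, and −6.7% becomes −2.7%.

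In a random-intercept model as in SAP 11.3, Year-9 GMCs under assumed titres were:

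| Yearly dropout | True | Floor | Post-booster missing |
|---|---|---|---|
| 0% | 0.42 | 0.27 | 0.43 |
| 5% | 0.44 | 0.28 | 0.45 |
| 10% | 0.42 | 0.28 | 0.43 |

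At 5% dropout, stopping the imputation at withdrawal barely changed the floor result (0.281 against 0.283). The floor itself drives the GMC bias, not the withdrawal clause.

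The direction can reverse. With very fast decay (Year-3 GMC 0.6, slope −0.12), the floor raised the crude GMC from 0.114 to 0.119 at Year 9 and from 0.092 to 0.110 at Year 10.

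**5. Protocol rule.** Excluding subjects after the booster in simple yearly summaries leaves mainly persisters: 95.6% against a true 62% at Year 9 in one assumed scenario.

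**The case against.** Counting a boosted subject as a failure is pre-specified and has a stated reason. There is no hypothesis, success criterion or power calculation. Protocol 8.4.3.3.3 calls the yearly % supplementary, and the Kaplan-Meier curve can check it. This limits the consequences, but it does not justify filling visits after withdrawal for one group only.

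A reader might infer more than the documents support:
- **That the primary comparison is biased.** It is not: values after the first titre <0.5 are not used there.
- **That the floor always lowers GMCs.** It does so only if boosted subjects' no-booster titres would average above 0.1. Triggers of 0.2–0.4 suggest a fall, but they are only three of five codes.
- **That the change was made silently.** The SAP history (11 June 2019) lists the imputation method. What it lacks is a statement that this departs from the protocol.
- **That the % is unbiased without dropout.** That is true for never having been observed <0.5. It need not hold for point prevalence: with assumed assay variation of 0.12 log10, a single low reading becomes permanent failure, and 61.3% fell to 52.5% at Year 9 with no dropout.
- **That <0.1 proves the extension assay's limit is 0.1.** The program covers both studies, so this is only a discrepancy to reconcile.
- **That reverting to the protocol's exclusion would cure the problem.** In simple yearly summaries it errs upward.

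**Conclusion.** The concern holds in this limited form and should be fixed. Under the SAP's own MCAR assumption, any non-zero dropout after some subjects have been boosted makes the yearly % ≥0.5 and the RCD curve at or above 0.5 too low. That direction is arithmetic. The size depends on dropout, which the documents do not give: the illustrations span about 1 to 5 points at 3% per year and 5 to 17 at 10%.

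Separately, and without any dropout, the RCD curve between 0.1 and 0.5 is pulled down for boosted subjects. The GMC is lowered when their no-booster titres would average above 0.1. Arm contrasts can shift either way. The affected results are secondary.

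**What to change.** 1. **Yearly % and RCD curve.** Stop the imputation at withdrawal, so that boosted and unboosted subjects leave the denominator by the same rule, and state the assumption of equal, non-informative dropout. This matters: in the middle case with unequal dropout (4% per year unboosted, 12% boosted), attended-only counting gave 76/59% against 69/49% by Kaplan-Meier. So report the planned Kaplan-Meier estimate at each year beside it, labelled as % never observed <0.5. It is a different quantity from point prevalence and counts from Day 57 of the parent study. It does not need equal dropout in the two groups.
2. **RCD curve below 0.5.** Mark it as not estimable for boosted subjects.
3. **GMC.** Add a mixed model with post-booster values set to missing and the observed triggering titre kept. State its missing-at-random assumption and show it beside the floor analysis. A richer covariance than "random intercept / subject = usubjid type = UN", or use of the parent-study Day 366 titre, is optional.
4. **Wording.** State one assay limit and use its half throughout. Align 8.2.2 with 8.8 on the triggering value. Correct the censoring sentence in 8.8, on which the Kaplan-Meier check depends. Label the departure from protocol 8.3.4 and 8.4.3.3.3.

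The cost is SAP wording, one derivation, one added model and a revised figure, with no new data. The downside is an added missing-at-random assumption and no RCD curve below 0.5 for boosted subjects.

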1. BACKGROUND AND RATIONALE

Data on persistence of adequate antibody concentrations (i.e. ≥ 0.5 IU/mL) for up to two years after immunization with *Rabipur* (Rabies, whole virus vaccine) was found in a limited number of pre-exposure prophylaxis (PrEP) studies where the conventional (vaccine administered on days 0, 7, 21 or 28) regimen was administered. There are no data available in literature about persistence of RVNA concentrations following the new, accelerated, one-week (vaccine administered on days 0, 3, 7) PrEP regimen. According to World Health Organization (WHO), booster doses are generally required every 2-5 years and there is no evidence on the best timing for booster administration after 5 years. For this reason, the onset, extent and duration of (sero)protection and the requirement for and timing of booster vaccination following a primary series according to an accelerated or a conventional PrEP Intramuscular (IM) regimen deserves further investigation.

The aim of this study is to evaluate the long-term (up to approx.10 years) persistence and to assess the boostability of immune responses in subjects who received a primary series of accelerated or conventional rabies PrEP IM regimen in V49_23 study.

For further details please refer to section 1.0 of the protocol.

History of changes:

Date	Description	Protocol Version
25 September 2015	First version	Version 1 – 23 February 2015
11 June 2019	Second version/amendment 1: Addition of a mixed model to account for repeated measures within subjects, with inclusion of SAS code. Extension of ± 14 days of the annual Scheduled Clinic Visit window for inclusion of subjects in the Per Protocol Set. Addition of details about subject disposition tables for the purpose of the Interim Analysis. Imputation method of immunogenicity data collected after the administration of a booster dose with application to the long persistence analysis. Modification of the protocol deviations and corresponding PD codes (to fit GSK codes). Details on how to deal with subjects who received a rabies booster dose after conclusion of V49_23 and beginning of V49_23E1 studies. Modification of information regarding the survival analysis: FAS-2 definition, SAS code.	Protocol Amendment 2 – 25 February 2019

Date	Description	Protocol Version

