7.7. Overview of Analysis Sets by PD Code

Table 4 Safety Sets: applicable to Exposed to Booster dose subjects only

PD code	PD Description and Exclusion Reasons	Study Objective/Period	Exposed Set	Safety Set	
			Exclusion code	EXPFL	SAFFL
1070	incomplete treatment course. Booster was not administered although subject had RVNA concentration of <0.5 IU/mL	All Study		EXC	EXC
2150	Subject did not provide any post-booster safety data	Approx. 6 months after booster exposure*			EXC

* For further details refer to study protocol

EXC = excluded from this analysis set.

Table 5 Immunogenicity Sets

PD code	PD Description and Exclusion Reasons	All ENROLLED	FAS 1	FAS 2	PPS 1	PPS 2
		Exclusion code	ENRFL	FAS10FL	FAS20FL	PPS10FL
800	Fraudulent data		EXC	EXC	EXC	EXC
900	Signed informed consent not available on site				EXC	EXC
900	Wrong informed consent version signed				EXC	EXC
900	Informed consent not signed and/or dated by subject				EXC	EXC
900	Informed consent not signed and/or dated by appropriate site staff.				EXC	EXC
900	Informed consent not signed prior to any study procedure (examples: a, b, c)				EXC	EXC
900	Other informed consent deviations				EXC	EXC
910	Partially or inappropriately signed ICF				EXC	EXC
1070	Booster was administered although subject had RVNA concentration ≥ 0.5 IU/mL			EXC	EXC	EXC
1070	Route of administration is wrong or unknown				EXC	
1070	Administration of booster vaccine at wrong visit				EXC	
1070	Commercial vaccine used in place of study vaccine (but same vaccine)				EXC	
1070	Study treatment administered while contraindication				EXC	
1070	Study treatment not prepared as per protocol (e.g. reconstitution)				EXC	
1070	Incorrect Volume was given				EXC	
1080	Use of study treatment impacted by a temperature excursion which was not reported or approved, or which was disapproved for further use.				EXC	
1090	Expired study treatment administered				EXC	
2010	Eligibility Criteria Not Met				EXC	EXC
2040	Prohibited concomitant medication (interval + type)				EXC	EXC
2040	Prohibited concomitant vaccination (interval + type)				EXC	EXC

PD code	PD Description and Exclusion Reasons	All ENROLLED	FAS 1	FAS 2	PPS 1	PPS 2
		ENRFL	FAS10FL	FAS20FL	PPS10FL	PPS20FL
2040	Other excluded medication, vaccine or device deviation				EXC	EXC
2090	Blood draw after booster dose outside 7 (+/- 1 day) day interval				EXC	EXC

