8.8. Derived and Computed Variables

Data from parent study (V49_23)

Time to event analysis

For time to event analysis (i.e., Kaplan-Meier (KM) and Cox proportional hazard regression model), immunogenicity data from parent study, from day 57 up to one year, as well as data related to time between the end of parent study and start of this study (i.e., if subject receives a booster between the two studies) will be considered, as estimation of time to RVNA concentration drop below 0.5IU/mL.

Long term immunogenicity analysis

Demographics

Race and Age at time of V49_23 enrolment will be derived from demography of the parent study.

Body Mass Index (kg/m²) (BMI) will be calculated using the following formula: Weight (kg) / Height² (m²)

Time to Event

Survtime represents time to event/censoring in years:

Survtime variable will be derived using the planned visit day at which the event occurred or the subject is censored as time point.

The following SAS code describes how to derive **Survtime** from V49_23 study and from the current study (V49_23E1).

```

DATA <dbname>;
  SET <dbname>;
  IF LBORRES IN ('<0.1', '0.1', '0.2', '0.3', '0.4')
  THEN DROP ='Y';
  ELSE DROP ='N';
  format LABEL $12.;
  IF STUDYID = 'V49_23' THEN DO;
    IF VISITNUM = 9 THEN do;POINT =1; YEAR =57; LABEL = 'Day 57'; end;
    IF VISITNUM = 10 THEN do;POINT =2; YEAR =91; LABEL = 'Day 91'; end;
    IF VISITNUM = 11 THEN do;POINT =3; YEAR =181; LABEL = 'Day
181';end;
    IF VISITNUM = 12 THEN do;POINT =4; YEAR =365;LABEL = 'Day 366';end;
  END;
  IF STUDYID = 'V49_23E1' THEN DO;
    IF VISITNUM = 1 THEN do; YEAR = 3*365; LABEL = 'Year 3'; end;
    IF VISITNUM = 2 THEN do; YEAR = 4*365; LABEL = 'Year 4'; end;
    IF VISITNUM = 3 THEN do; YEAR = 5*365; LABEL = 'Year 5'; end;
    IF VISITNUM = 4 THEN do; YEAR = 6*365; LABEL = 'Year 6'; end;
    IF VISITNUM = 5 THEN do; YEAR = 7*365; LABEL = 'Year 7'; end;
    IF VISITNUM = 6 THEN do; YEAR = 8*365; LABEL = 'Year 8'; end;
    IF VISITNUM = 7 THEN do; YEAR = 9*365; LABEL = 'Year 9'; end;
    IF VISITNUM = 8 THEN do; YEAR = 10*365; LABEL = 'Year 10';end;
  END;
  Survtime= YEAR;

  IF DROP ='Y' THEN CENSOR=1; ELSE CENSOR = 0;
RUN;

```

Censor: represents censoring indicator variable: 0=censored, 1=event of interest;

Event of interest: RVNA concentration < 0.5 (censor=1)

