If one of the followings occur, subject will be censored (censor=0) and time to the last data available strictly before the event will be included in the survival analysis:

- Subject is lost to follow up
- Subject withdraws consent
- RVNA concentration not available for last visit (last visit could differ from the final visit)
- Subject receives booster (study vaccine or another rabies vaccine) but RVNA concentration ≥ 0.5 or unknown
- Subject performs final visit (i.e., study termination visit) and RVNA concentration is ≥ 0.5 IU/mL (for the purpose of the IA, if visit 4 is completed by the subject he will be considered as a censored value at the time of visit 4)

The subjects will be considered as censored if any of the following event occurs before the subject's antibody titer level goes beyond the level of 0.5IU/mL:

- All further blood draw results are missing

Censor variable will be set to 0 if any of the case above occurs. If the subject's antibody level titer goes beyond 0.5 IU/mL censoring values will be set to 0 at the time of the 1st antibody titer level below 0.5 IU/mL.

Point Variable describes the order of RVNA concentration observed. It will be POINT=5 if a subject receives booster between V49_23 END (last visit date) and V49_23E1 START (first visit date).

Immunogenicity

Values below the limit of quantification (recorded as “< LQ”) will be set to half that limit (i.e., LQ/2]).

Geometric Mean Concentration

The GMC will be calculated using the following formula:

$$10^{\left[\frac{\sum_{i=1}^n \log_{10}(t_i)}{n} \right]}$$

where t_1, t_2, \dots, t_n are n observed immunogenicity titers/concentrations.

Geometric Mean Ratio

Geometric mean ratios (GMRs) measure the changes in immunogenicity concentrations *within* subjects.

The GMR will be calculated using the following formula:

$$10^{\left[\frac{\sum_{i=1}^n \log_{10}\left(\frac{v_{ij}}{v_{ik}}\right)}{n} \right]} = 10^{\left[\frac{\sum_{i=1}^n \log_{10}(v_{ij}) - \log_{10}(v_{ik})}{n} \right]}$$

where, for n subjects, v_{ij} and v_{ik} are observed immunogenicity titers/concentrations for subject i at time-points j and k , $j \neq k$.

Imputation of RVNA concentration in subjects receiving a booster

Once a subject receives a rabies vaccine booster dose (i.e. RVNA<0.5) he/she will be treated as follows:

Time to event analysis:

Censor=1 for the time-point in which RVNA is observed being below 0.5 IU/mL

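### SAP 7.3 drops a subject's valid pre-booster annual values from the long-term GMC, percentage and reverse cumulative distribution analyses when a booster is given while RVNA was still above 0.5 IU/mL

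*SAP*

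**What the plan says.** **Exclusion.** SAP 7.3 states that when a subject is boosted before or after entry, "but the last known RVNA value was above 0.5 IU/mL, then he/she will be excluded from the long term immunogenicity analysis set". Its reason is that values recorded after the booster would inflate persistence, and that imputing them as failures would be wrong because the subject had not fallen below 0.5 IU/mL. SAP 8.8 adds that subjects boosted outside the study, "for which RVNA value at the time of booster vaccination is not available will be excluded from FAS-2 and PPS-2". In SAP 7.7, Table 5, the code 1070 row "Booster was administered although subject had RVNA concentration ≥ 0.5 IU/mL" appears to carry an exclusion flag under FAS-2, although the table's alignment is imperfect as extracted. SAP 6.1 allows a major deviation to remove only part of a subject's data.

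**Boosters given below 0.5 IU/mL.** For the long-term persistence analysis of these subjects, SAP 8.8 says "All immunogenicity data until booster will be part of analysis as they are reported". Later values are replaced by 0.1 IU/mL.

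**Protocol.** For GMCs, percentages and reverse cumulative distribution plots, Protocol 8.3.4 removes a subject only after the booster, and Protocol 8.4.3.3.3 repeats this for the GMCs. Protocol 8.3.4 leaves further details of the sets to the SAP.

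**Time to event.** SAP 8.8 censors in this case: "Subject receives booster (study vaccine or another rabies vaccine) but RVNA concentration ≥ 0.5 or unknown". It also says that "time to the last data available strictly before the event will be included in the survival analysis". SAP 11.2 names no analysis set for Kaplan-Meier or Cox.

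**The concern.** The stated reason justifies removing post-booster values. It gives no ground for removing values measured before the booster, which reflect the primary series alone and are what the secondary objective asks about.

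The two booster rules then treat earlier data differently according to the outcome. A subject who fell below 0.5 IU/mL keeps the earlier annual values. A subject who had not fallen, and was boosted for travel or work, loses them. Those removed were all at or above 0.5 IU/mL at every earlier annual visit (leaving aside anyone with an earlier drop). Early-year GMCs, percentages and distribution curves are therefore pulled downwards by an event that happened later.

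**Working it through.** **Who is affected.** The annual values run from Year 3 to Year 10.
- Booster between the parent study and entry: no annual value precedes it, so none is lost.
- Booster after entry: every annual value up to the booster is lost. With boosters spread evenly over the seven intervals from Year 3 to Year 10, the mean number lost is (1+2+…+7)/7 = 4. Simulation with subjects still event-free gives 3.7 to 4.0.

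**Inputs.** From the documents: at most 578 subjects (158 + 209 + 211) and 8 annual visits, so 578 × 8 = 4,624 planned values. Assumed, because the documents give no figures: a share q of 1, 2 or 5% boosted after entry with no earlier value below 0.5 IU/mL; an exponential time to the drop below 0.5 IU/mL; true Year 10 persistence S of 0.90, 0.70 or 0.50.

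**Year 3 percentage.** The true proportion at Year 3 is p = S^0.3, that is 0.9689, 0.8985 or 0.8123. All removed subjects are at or above 0.5 IU/mL at Year 3, so whole-subject exclusion gives (p − q)/(1 − q). The shortfall is q(1 − p)/(1 − q).

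| q | Subjects of 578 | S = 0.90 | S = 0.70 | S = 0.50 |
|---|---|---|---|---|
| 1% | 6 | 0.03 points | 0.10 | 0.19 |
| 2% | 12 | 0.06 | 0.21 | 0.38 |
| 5% | 29 | 0.16 | 0.53 | 0.99 |

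For example, at q = 5% and S = 0.50: 0.05 × 0.1877/0.95 = 0.0099.

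**Later years at q = 5%, by simulation.** The shortfalls for S = 0.90, 0.70 and 0.50 are 0.19, 0.59 and 1.02 points at Year 5, and 0.16, 0.46 and 0.75 at Year 7. At Year 10 the shortfall is zero, because under either rule these subjects no longer contribute a value.

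**Values lost at q = 5%.** About 107 to 113 of 4,624, or 2.3 to 2.4%.

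**Year 3 GMC at q = 5%.** Assume log10 titres are normal with SD σ. The mean of those above the threshold exceeds the overall mean by σλ, with λ = φ(z)/p and z the normal quantile of p. Exclusion lowers the log10 mean by qσλ/(1 − q).
- p = 0.9, σ = 0.4, λ = 0.195: 0.0526 × 0.4 × 0.195 = 0.0041, so the GMC is 0.9% lower.
- p = 0.7, σ = 0.6, λ = 0.497: 0.0526 × 0.6 × 0.497 = 0.0157, so the GMC is 3.5% lower.

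**Against sampling error.** With 209 subjects and no dropout, the 95% half-width of the Year 3 percentage, 1.96√(p(1 − p)/209), is 2.3 points at p = 0.9689 and 5.3 points at p = 0.8123. The shortfalls at q = 5% are 0.16 and 0.99.

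**The case against.** **The protocol delegates set details to the SAP.** It does, and the SAP has already replaced the protocol's post-booster removal with imputation for boosters below 0.5 IU/mL. The departure from the protocol is therefore not decisive alone. What stands is that the SAP's own reason does not cover the values it discards.

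**These subjects are protocol deviators.** Non-study rabies vaccine is an exclusion criterion before each Scheduled Visit (Protocol 4.2). But Table 5, as extracted, handles eligibility failures and prohibited vaccination (codes 2010 and 2040) in the per-protocol sets only. The deviation does not make earlier values invalid for the full analysis set.

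**The repair is incomplete in late years.** This stands. Subjects boosted below 0.5 IU/mL remain as imputed failures while the others go missing, and Year 10 is the same under both rules. The gain is in the early and middle years.

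**A stronger reading.** A reader might infer that SAP 7.3 contradicts SAP 8.8 for the primary time-to-event analysis, leaving its population undefined or biased. The documents do not support that. Protocol 8.4.2.3.2 lists the All Enrolled Set and FAS-1 for the primary immunogenicity objectives, and Protocol 8.4.3.3.2 gives FAS-2 to the secondary objective. The time-to-event set in Protocol 8.3.4 has no such exclusion. SAP 8.8 brings boosters given between the studies into the survival data and states how to censor. Against this stands one line in the SAP's history of changes, "Modification of information regarding the survival analysis: FAS-2 definition, SAS code", which is not an operative rule.

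Nor would it be safe to argue that censoring is always the better rule. In a simulation with a base booster rate of 2% per year and true Year 10 persistence of 0.700 and 0.501, boosting was made three times as likely in the two years before the drop. Censoring gave 0.715 and 0.520; exclusion gave 0.693 and 0.489, which is closer to the truth.

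**Conclusion.** The point holds for the secondary long-term analyses and is minor. Whole-subject exclusion from FAS-2 discards valid pre-booster annual values of subjects boosted after entry, and only of those who had not fallen below 0.5 IU/mL. Early-year persistence is understated.

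At an assumed 5% boosted after entry, the Year 3 percentage is lower by about 0.2 to 1.0 points and the Year 3 GMC by about 0.9 to 3.5%, with nothing at Year 10. At 1% the Year 3 percentage shortfall is 0.03 to 0.19 points. These sizes rest on assumed booster rates, persistence and titre spread, and the percentage shortfalls lie inside sampling error. The direction does not depend on those assumptions for subjects with no earlier value below 0.5 IU/mL. The Table 5 flag is weaker evidence than SAP 7.3 and 8.8, because it may mean only part of a subject's data.

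For Kaplan-Meier and Cox, the governing reading is enrolled subjects with the SAP 8.8 censoring. SAP 11.2 needs a clarifying line, not a change of method.

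**What to change.** 1. In SAP 7.3, in the SAP 8.8 sentence on unknown RVNA, and in the FAS-2 cell of Table 5 code 1070, replace the exclusion with this rule: a subject with no earlier RVNA below 0.5 IU/mL who is boosted when the last RVNA was at or above 0.5 IU/mL, or unknown, stays in FAS-2 with all values before the booster; later values are set to missing in the GMC, percentage and reverse cumulative distribution analyses. A subject with an earlier value below 0.5 IU/mL keeps the existing handling. Use at or above 0.5 IU/mL throughout, since SAP 7.3 says only above.
2. Limit the imputation sentences in SAP 8.2 (GMC and percentages) and the note in SAP 11.3 to boosters given because RVNA was below 0.5 IU/mL, as SAP 7.3 and 8.2.2 already do. Otherwise the retained subjects would be imputed as failures.
3. In SAP 11.2, state that Kaplan-Meier and Cox use enrolled subjects with RVNA data (Protocol 8.3.4 and 8.4.2.3.2), censored under SAP 8.8 at the last value before such a booster, without the SAP 7.3 exclusion.
4. Report the number and timing of these boosters by arm. SAP 10.1 covers only those before entry. Give whole-subject exclusion as a sensitivity analysis, because censoring is also biased if boosting is related to titre.
5. In SAP 8.8, the sentence that sets the censoring variable to 0 at the first titre below 0.5 IU/mL should say 1, to match the SAS code.

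The cost is SAP wording, one table cell and flag programming, with no new samples. Boosters between the studies are already recorded (Protocol 6.5). For outside boosters after entry, the date would have to come from the eligibility check at each Scheduled Visit or from the deviation record, because Protocol 3.4.1 limits concomitant medication data to those linked to an SAE.
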